## Risks

- Prospective participants who consent to participate in the study will be asked questions about their substance use, which may be uncomfortable. This research is covered by a Certificate of Confidentiality (CoC) from the National Institutes of Health. This means that the researchers cannot release or use information, documents, or samples that may identify participants in any action or suit unless they say it is okay. They also cannot provide them as evidence unless the participant has agreed. This protection includes federal, state, or local civil, criminal, administrative, legislative, or other proceedings. An example would be a court subpoena. The CoC is automatic with NIH funding.
- Although unlikely, a breach of confidentiality could occur. Signed informed consent forms will be stored separately from all collected data in a different locked cabinet in a locked office at the Vermont Center on Behavior and Health, which is located in the University of Vermont Medical Center, UHC campus.
- Participants in this study may experience withdrawal. These symptoms can include anger, irritability, frustration, anxiousness, depressed mood, substance cravings, difficulty concentrating, sleep problems, restlessness, impatience, constipation, dizziness, nightmares, and nausea. If these mood changes appear to put a participant's health at risk, they will be asked to stop participating in the study. We will be providing a resources sheet about withdrawal services available to each participant (and other services available) when they complete the informed consent. Additional copies will also be available for participants throughout the study.

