**Note:** A clinical research protocol may involve interventions that are strictly experimental or it may involve some aspect of research (e.g., randomization among standard treatments for collection and analysis of routine clinical data for research purposes). It is important for this section to distinguish between interventions that are experimental and/or carried out for research purposes versus those procedures that are considered standard therapy. In addition, routine procedures performed solely for research purposes (e.g., additional diagnostic/follow-up tests) should be identified.

All study procedures are for research purposes only. This will be an experimental study conducted at Safe Recovery at the Howard Center. All study procedures will take place in a private, designated room at Safe Recovery. [name], our co-investigator and collaborator on the project, is the program manager at Safe Recovery who has authorized and set aside this room as research space to be used for this study. Individuals receiving services at the Howard Center Safe Recovery will be approached for participation by a center staff member; this particular staff member's primary role at the Howard Center is to assist with research. This staff member is listed as a study team member in UVMClick, has a UVM netid, and has completed CITI training. Potentially eligible participants will be asked when they come in for services if they would like to participate in a research study. The research assistant will complete each step in the consent process documentation form (listed in the additional materials). Prospective participants who consent to participate in the study will move on to the screening procedure next. Participants will also be provided with the "Resources Sheet" at the same time as the informed consent.

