Participant baseline demographics and characteristics will be compared between treatment conditions (Health Education vs. health Education plus Incentives for Abstinence) using Chi Square Tests of Independence or Fisher's Exact Tests for categorical variables and Wilcoxon Rank Sum Tests or Two-Sample T-tests for continuous variables, depending on the distributions of the variables. If a specific characteristic differs significantly between treatment conditions and is predictive of the outcome, it will be considered as a potential covariate in subsequent analyses. The primary outcome to be analyzed will be point-prevalence stimulant abstinence, which will be determined by percentage of negative urine samples for stimulants using a point-of-care test. Analyses of treatment condition effect on point-prevalence stimulant abstinence will adhere to an intent-to-treat approach whereby all participants randomized to each treatment condition will be included in the analyses independent of early dropout, noncompliance, etc. Point-prevalence abstinence rates will be compared between treatment conditions at individual timepoints using Chi Square Tests of Independence. Comparisons of point-prevalence abstinence rates between treatment conditions across all assessments will be analyzed using mixed model repeated measures for categorical data based on generalized estimating equations (GEE) using a logistic link function. Comparisons of predictors of abstinence that are continuous outcomes and continuous outcomes based on survey responses between treatment conditions across all assessments will be analyzed using mixed model repeated measures analyses of variance. Comparisons of predictors of abstinence that are categorical outcomes and categorical outcomes based on survey responses between treatment conditions across all assessments will be analyzed using mixed model repeated measures for categorical data based on generalized estimating equations (GEE) using a logistic link function.

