Participants are free to withdraw from the study at any time and for any reason while they are completing the study. Participants may be withdrawn if the PIs determine it is not advisable that they continue on in the study. Regarding data analysis, we will adhere to an intent-to-treat approach (Armitage, 1983) wherein all participants randomized to the study conditions will be included in the analyses independent of early dropout, or noncompliance.

**Sources of Materials:** Identify sources of research material obtained from individually identifiable human subjects in the form of specimens, records or data. Indicate whether the material or data will be obtained specifically for research purposes or whether use will be made of existing specimens, records or data.

All data collected will be for research purposes only. This study will include individuals 18 years and older who participate in services provided by Safe Recovery at the Howard Center in Burlington, VT. The data collected will include both answers to the questionnaires described above and urine specimens which will be tested for psychomotor stimulants. Thus, the sources of materials include:

- Questions on sociodemographic, substance use history, and substance use follow-back
- Questions on demand for substances, decision making, and substance craving
- Urine samples to be tested for recent stimulant use

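### Safety stops are worded as leaving the study, with no provision for outcome data afterwards, so later results would be lost, plausibly not at random

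*Combined protocol and SAP*

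**What the plan says.** Four parts of the combined protocol and SAP bear on this.

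- **Risks.** The list warns that "Participants in this study may experience withdrawal", describes mood and other symptoms, and says of people whose health these mood changes seem to endanger that "they will be asked to stop participating in the study". The object is the study, not the incentives or the education sessions.
- **Withdrawal Procedures.** "Participants may be withdrawn if the PIs determine it is not advisable that they continue on in the study". The form's prompt asks what the study requires when a subject withdraws. The answer says nothing about urine tests or questionnaires after that point. It then commits to intent-to-treat: "all participants randomized to the study conditions will be included in the analyses independent of early dropout, or noncompliance".
- **Statistical Considerations.** The same commitment appears for the primary outcome: "all participants randomized to each treatment condition will be included in the analyses independent of early dropout, noncompliance, etc". That outcome is "point-prevalence stimulant abstinence, which will be determined by percentage of negative urine samples for stimulants using a point-of-care test". It is compared by chi-square tests at single timepoints and by GEE with a logistic link across assessments. No rule is given for samples that were not obtained.
- **Procedures.** "All study procedures are for research purposes only". Sources of Materials likewise lists only study questionnaires and study urine samples, so no other source of outcome data is described.

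**The concern.** Because outcomes come only from study procedures, a participant who leaves the study on safety grounds stops producing them. That person remains in the analysis set but has no results at the later timepoints.

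The reason for the stop makes these gaps hard to treat as random. The trigger is a set of withdrawal symptoms, which plausibly accompany cutting down or stopping use. Only the incentive arm is paid for negative samples, so such stops could also be more frequent there. If so, the missing results would be related to both the outcome and the arm. Unweighted GEE on the observed samples is in general valid only when missingness is completely random or depends on covariates in the model. Scoring missing samples as positive is a guess at results that could have been sought.

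The protocol wants the pilot to inform a larger trial, so its effect estimate and its account of who stopped and why both matter. The acceptability questionnaire, due at week 12 or shortly after, would probably also be missed by anyone stopped before then.

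**Working it through.** **1. Which data end at a stop.** Risks and Withdrawal Procedures describe exit from the study. Procedures and Sources of Materials describe no outcome data outside it. No section provides for collection after an exit. Loss of later data is therefore the natural consequence of the wording, although the protocol does not state it.

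**2. Does this contradict intent-to-treat?** Both intent-to-treat statements expressly anticipate dropout. A participant stopped after week 4 may already have given up to 4 × 2 = 8 samples, and these enter the GEE. The person is not removed from the analysis. The later timepoints are what is lost.

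**3. Scheduled samples.** Intervention Conditions and Data Collection give two samples a week for 12 weeks: 2 × 12 = 24 per participant. The plan's control-arm payment maximum agrees: $240 / $10 = 24. Assuming 40 participants split equally (the allocation ratio is not stated), the incentive arm has 20 × 24 = 480 scheduled samples.

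**4. Effect on the arm's percentage of negative samples.** Assume *k* incentive-arm participants are stopped after week 4, would have stayed negative, and have missing samples scored positive. Each loses weeks 5 to 12, or 8 × 2 = 16 samples. The loss is 16*k*/480.

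| Stops *k* | Samples lost | Fall in percentage negative |
|---|---|---|
| 1 | 16 | 16/480 = 3.3 points |
| 2 | 32 | 32/480 = 6.7 points |
| 3 | 48 | 48/480 = 10 points |

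**5. Effect at a single timepoint.** Let *a* and *c* be the numbers of incentive and control participants, out of 20 each, who are truly abstinent at week 12, and let *k* abstinent incentive-arm participants be stopped. Scoring missing as positive gives (*a* − *k*)/20 − *c*/20. Using observed data only gives (*a* − *k*)/(20 − *k*) − *c*/20. Both assumed cases below have a true difference of 20 points.

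| *k* | Missing = positive (either case) | Observed only, 10/20 vs 6/20 | Observed only, 6/20 vs 2/20 |
|---|---|---|---|
| 1 | 15 | 9/19 − 6/20 = 17.4 | 5/19 − 2/20 = 16.3 |
| 2 | 10 | 8/18 − 6/20 = 14.4 | 4/18 − 2/20 = 12.2 |
| 3 | 5 | 7/17 − 6/20 = 11.2 | 3/17 − 2/20 = 7.6 |

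**6. The direction is not fixed.** Take 10/20 vs 6/20 and suppose the one person stopped would have been using at week 12. Scoring that sample positive is then correct (20 points), while observed data only gives 10/19 − 6/20 = 22.6 points. Which handling is biased, and which way, depends on results that the current wording would leave uncollected.

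**The case against.** The sentence in Risks is participant-protection language, not a data-collection rule, and the withdrawal section says only that people may be withdrawn. The consent form was not available for this review and may say more about follow-up. The symptom list names neither an arm nor a drug, and the protocol's background notes that clients of the service may inject opioids or other drugs, so the symptoms need not come from reduced stimulant use. The trigger is narrow, and this is an exploratory pilot of 40. The wider gap is the absence of any rule for missing samples, which affects voluntary dropout and missed visits as well.

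Much of this stands, and it rules out three stronger readings that a reader might infer:

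- *That the safety stop contradicts the intent-to-treat promise, or that leaving the missing samples out breaks it.* The promise anticipates dropout, and samples given before the stop stay in the GEE.
- *That missing data related to arm and abstinence are built into the design.* The link is reasoned from the trigger and the payment scheme. No section documents it.
- *That a loss of 10 points is to be expected.* That figure needs three stops, all in one arm, all in people who would have stayed negative, and all missing samples scored positive. The documents give no stop rate.

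A practical objection also stands: continued collection needs more than a sentence. Under Compensation for participation, incentive-arm urine samples are paid only when negative, while control samples are paid for being provided. After a stop, an incentive-arm participant would have no defined urine payment.

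The core remains. No section provides for outcomes after a safety stop, and a missing-data rule could only assume what an invitation to continue assessments might have observed.

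**Conclusion.** The point holds as an inexpensive improvement. As worded, safety stops are exits from the study, and outcomes after them would be lost at the later timepoints for people stopped because of withdrawal symptoms. That loss is plausibly informative. Whether it is more common in the incentive arm is a possibility only.

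The size is unknown and may be nil if nobody is stopped. Under the stated assumptions, each stop costs 3.3 points of the incentive arm's percentage of negative samples when missing counts as positive. At week 12, one stop of an abstinent incentive-arm participant moves an assumed true 20-point difference to 15 points on that scoring, or to between 16.3 and 17.4 points on observed data. These are illustrations, not forecasts. No view is taken on the clinical stopping rule.

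**What to change.** Reconcile Risks, Withdrawal Procedures and Statistical Considerations by separating the end of the intervention from the end of data collection:

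1. Leave the decision to stop entirely with the investigators.
2. State that a stopped participant may, with consent and unless the investigator judges contact unsuitable, still be invited to the scheduled urine tests and the week 4, 8 and 12 questionnaires.
3. Record the date and reason for each stop, and report them by arm.
4. State how urine samples after a stop are paid in each arm. The questionnaires already carry $10 each.

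The cost is some extra contact effort, a small payment cost and a change to the consent wording. For scale only, 16 remaining samples at the control arm's existing $10 would come to $160 per person stopped after week 4. The change reduces potentially informative gaps. It does not replace a stated rule for missing samples, which is still needed for people who decline further contact.

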## Benefits

- The primary benefit is that participation could result in abstinence or reduced use of psychomotor stimulants. This would have numerous positive health benefits for the participant. This study may also teach us how to more effectively help others stop using stimulants. The other information that participants provide may increase knowledge about factors that influence the ability to quit using stimulants.

**Therapeutic Alternatives:** List the therapeutic alternatives that are reasonably available that may be of benefit to the potential subject and include in the consent form as well.

Not Applicable

Participants could attempt to stop or reduce their stimulant use on their own, without support offered by participation in the study.

**Data Safety and Monitoring:** The specific design of a Data and Safety Monitoring Plan (DSMP) for a protocol may vary extensively depending on the potential risks, size, and complexity of the research study. For a minimal risk study, a DSMP could be as simple as a description of the Principal Investigator's plan for monitoring the data and performance of safety reviews or it could be as complex as the initiation of an external, independent Data Safety and Monitoring Board (DSMB). The UVM/UVM Medical Center process for review of adverse events should be included in the DSMP.

All efforts will be made to maintain confidentiality. The IRB at UVM will review this protocol. Oversight of the project and monitoring will be conducted by the primary investigators ([name] and [name]). All procedures will be monitored to ensure adherence with the protocol. All assessments will be conducted privately. All questionnaires will be administered on paper. A hard copy of the collected data will be stored in a locked office within a locked file cabinet. All hard copy questionnaire data does not contain any directly identifiable information. Hard copy data will be inputted into, and directly stored on, a secure web platform, REDCap. All data will be coded by identification number, with the codes known only by the investigators on this project. Names will not be connected with any results. The monitoring plan will consist of ongoing, close monitoring of data and safety issues by the PI and other project staff and prompt reporting of any adverse events (AEs) or serious adverse events (SAEs) to the institutional review board and/or NIGMS. The security of these records will be maintained by keeping paper files in a locked file cabinet and by keeping computer files in a password protected file on REDcap. The results of this study

will eventually be published, but patient confidentiality will be maintained.

Define criteria to be used for decision making regarding continuation, modification, or termination of the entire study (not individual participation) (i.e. "stopping rules").

We plan to continue this study until the sample size has been met, after which the study will be terminated.

**What will be the frequency of the review?** Please note that the frequency of reviews should be commensurate with the risk of the study. At a minimum, a review of the data should be conducted annually at time of continuing review. **Forward copies of the data and safety monitoring reports to the 1) IRB, 2) CRC (if applicable), and/or 3) UVMCC (if applicable).**

Monthly  
 Quarterly  
 Bi-annually

Annually  
 Other (e.g. by dosing level, no. of subjects enrolled): \_\_\_\_\_

**Will the sponsor be conducting data monitoring visits for this study?**

Yes       No       NA

If yes, how often?

**Adverse Event, Unanticipated Problem (UAP), Reportable New Information (RNI):** Describe how events and UAPs will be evaluated and reported to the IRB. All protocols should specify that, in the absence of more stringent reporting requirements, the guidelines established in the "Adverse Event and Unanticipated Problems Reporting Policy" will be followed. The UVM/UVM Medical Center process for review of adverse events and UAPs to subjects or others should be included in the DSMP.

The primary investigators will evaluate all AEs, UAPs, and RNIs. We will follow the guidelines established by the Committees on Human Research "Adverse Event and Unanticipated Problems Reporting Policy". Any SAE will be brought to the attention of the PIs as soon as possible and no longer than 24 hours. Any AE or SAE that is both unexpected and related to study participation will be reported to the IRB within 7 days of the event. The IRB will make a determination as to whether additional reporting requirements are needed. IRB actions will be reported to the funding agency by the PIs no less than annually and more frequently as recommended by the local IRB. Any SAEs will be summarized in the yearly Progress Reports to the funding agency, including a review of frequency and severity. All SAEs will be followed through ongoing consultation with the physician caring for the patient until they resolve, result in death, or stabilize and are not expected to improve. The study staff will be in close contact with participants and health care providers throughout the study to monitor for potential unanticipated problems. Any unanticipated problems will be discussed at the weekly research staff meetings and reported as required to the CHRBSS using the Report of Protocol-Related Problems & Deviations Form.

**Withdrawal Procedures:** Define the precise criteria for withdrawing subjects from the study. Include a description of study requirements for when a subject withdraws him or herself from the study (if applicable).

Participants are free to withdraw from the study at any time and for any reason while they are completing the study. Participants may be withdrawn if the PIs determine it is not advisable that they continue on in the study. Regarding data analysis, we will adhere to an intent-to-treat approach (Armitage, 1983) wherein all participants randomized to the study conditions will be included in the analyses independent of early dropout, or noncompliance.

**Sources of Materials:** Identify sources of research material obtained from individually identifiable human subjects in the form of specimens, records or data. Indicate whether the material or data will be obtained specifically for research purposes or whether use will be made of existing specimens, records or data.

All data collected will be for research purposes only. This study will include individuals 18 years and older who participate in services provided by Safe Recovery at the Howard Center in Burlington, VT. The data collected will include both answers to the questionnaires described above and urine specimens which will be tested for psychomotor stimulants. Thus, the sources of materials include:

- Questions on sociodemographic, substance use history, and substance use follow-back
- Questions on demand for substances, decision making, and substance craving
- Urine samples to be tested for recent stimulant use

### **DRUG INFORMATION**

Investigators are encouraged to consult the UVM Medical Center Investigational Pharmacy Drug Service ([name]) prior to finalizing study drug/substance procedures.

**Drug (s)**

**Not applicable**

Drug name – generic followed by brand name and common abbreviations. Availability – Source and pharmacology; vial or product sizes and supplier. If a placebo will be used, identify its contents and source.

Preparation: Reconstitution instructions; preparation of a sterile product, compounded dosage form; mixing guidelines, including fluid and volume required. Identify who will prepare.

Storage and stability – for both intact and mixed products.

Administration – Describe acceptable routes and methods of administration and any associated risks of administration.

Toxicity – Accurate but concise listings of major toxicities. Rare toxicities, which may be severe, should be included by indicated incidence. Also, adverse interactions with other drugs used in the protocol regimen as well as specific foods should be noted. Address significant drug or drug/food interactions in the consent form as well. List all with above details.

Is it FDA approved: (include FDA IND Number)

1. in the dosage form specified? If no, provide justification for proposed use and source of the study drug in that form.

2. for the route of administration specified? If no, provide justification for route and describe the method to accomplish.

3. for the intended action?

